# Recommended algorithm for physician directed analgesia (PDA) arm:

- o IV Hydromorphone 0.4 mg Q4H PRN for pain 4-6
- o IV hydromorphone 0.6 mg Q2H PRN for pain 7-10
- Rescue IV hydromorphone 0.4 mg Q2H PRN for pain 4-10 = only to be given as a 'rescue dose' if patient has persistent pain despite using Q4H PRN IV hydromorphone (breakthrough pain)
- o Maximum opioid dosing: 1 mg per hour and 3 mg of IV hydromorphone per 4 hours
- If patient has received more than 2 rescue doses for breakthrough pain in 12 hours or is in uncontrolled pain: Hospitalist's recommended step-up orders: IV hydromorphone 0.8 mg Q4H PRN 4-6

## Recommended algorithm for patient controlled analgesia (PCA) arm:

- IV Hydromorphone 0.1 mg Q10 minutes
- Rescue IV hydromorphone 0.4 mg Q2H PRN for pain 4-6, hydromorphone 0.6 mg Q2H PRN for pain 7-10 = only to be given as a 'rescue' dose for if patient has persistent pain despite using PCA (breakthrough pain)
- Maximum opioid dosing: 1 mg per hour and 3 mg of IV hydromorphone per 4 hours
- If patient has received more than 2 rescue doses for breakthrough pain in 12 hours or is in uncontrolled pain: Hospitalist's recommended step-up orders: IV hydromorphone 0.2 mg Q10 minutes

# Recommended for all patients:

PO Acetaminophen 1000 mg Q8H scheduled

- IV Naloxone 40-80 mcg PRN for respiratory depression (RR<10) or significant somnolence
- PO Benadryl 25mg Q4H PRN moderate to severe pruritis
- Recommended algorithm for transition to oral:
- PO Oxycodone 5mg Q4H PRN for pain 4-6
- PO Oxycodone 10mg Q4H PRN for pain 7-10
- Rescue PO Oxycodone 5mg Q2H PRN for pain 4-10 = only to be given as a 'rescue dose' if patient has persistent pain despite using Q4H PO oxycodone (breakthrough pain)
- Dosing and frequencies of medications in the above algorithms are recommendations. The recommended doses are not required for maintenance in the study and we anticipate that they may change given patient characteristics and variable response to medication, the rapidly evolving nature of acute pancreatitis, and hospitalist preferences. However, the mode of IV opioid administration (PDA vs PCA) should remain as assigned until transition to PO opioid.
- Each patient will be closely monitored for adverse events related to opioid
  administration to include cardiorespiratory decompensation, hemodynamic
  instability, nausea, vomiting, confusion, altered mental status, headache,
  drowsiness, etc. This monitoring will include continuous pulse oximetry in addition to
  vital sign measurement every 4 hours.
- The efficacy of each treatment arm to adequately control the patient's pain will be assessed with scheduled use of the Numeric Rating Scale (NRS) every 4 hours by the nursing staff. Pain rating on the NRS will be documented by the nursing staff after each assessment. In an NRS, patients are asked to circle the number between 0 and 10 that fits best to their pain intensity. Zero usually represents 'no pain at all' whereas 10 represents 'the worst pain ever possible'.
- Likert scale of 1 to 10 (1 = Very poor, 10= excellent) will be used to grade overall patient satisfaction with pain control.
- Once each patient's pain is well controlled on IV opioid administration (as determined by the attending physician) and they can tolerate intake by mouth, transition from IV to PO opioid medication can be made in each arm by the attending physician. If the patient is unable to tolerate either the PDA or the PCA arm for any reason and requires switching over to the other arm as part of his/her clinical care, they will be withdrawn from the study and their data will be excluded while analyzing the results. AP has a variable course and may require IV opioids

after transition to PO opioids. The modality of IV opioid administration will revert to the assigned treatment arm.

- Other aspects of each patient's routine clinical care will continue as per the attending physician under whom the patient is admitted regardless of treatment arm status (PDA vs PCA).
- At the end of their hospital stay, we will document the following outcomes:
  - 1. Primary outcome: Length of stay (days)
  - 2. Secondary outcomes:
  - a. Number of hours the patient is NPO before diet is initiated
  - b. Mean pain scores on NRS over the first 24 hours, second 24 hours and course of their hospital stay
  - c. Total opioid dose for pain control during hospitalization (average MME during hospital stay)
  - d. Time to transition to PO opioids
  - e. Opioid-related adverse events/side effects: respiratory decompensation, sleep-disordered breathing, hypotension, nausea, vomiting, constipation, drowsiness, confusion, delirium or other mental status changes, myoclonus, headache, urinary retention, physician suspected opioid abuse or any form of allergic reaction.
  - f. Use of naloxone and antiemetics
  - g. Number of rescue doses required daily and in total through the hospital stay
  - h. ICU transfer
  - i. 30-day readmission rates
  - j. All-cause inpatient mortality and opioid-related inpatient mortality
  - k. 30-day mortality
  - I. Daily MME on discharge
- We expect to enroll patients over a 36-month period from the start date of the study. Based on this, we expect patient enrollment to end by 4/30/2024. We will plan to perform data analysis at two points: 1. Interim data analysis at a predetermined point in the study (mid-point of study), and 2. At the end of the study once patient enrollment has been completed.

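### Symptom adverse events are compared between arms without a common assessment schedule, so they may be recorded unequally; direction and size cannot be determined from the documents

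*Combined protocol and SAP*

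**What the plan says.** **Monitoring (B3.A, Recommended for all patients).** The plan states: "Each patient will be closely monitored for adverse events related to opioid" administration, and names nausea, vomiting, confusion, altered mental status, headache and drowsiness among them. It then gives the components: "This monitoring will include continuous pulse oximetry in addition to" "vital sign measurement every 4 hours". Efficacy is assessed by "scheduled use of the Numeric Rating Scale (NRS) every 4 hours by the nursing staff"; this asks about pain only. Section B5 again describes monitoring in terms of vital signs taken by nursing staff.

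**Outcome (B3.A, secondary outcome e).** The list is longer than the monitoring list. Besides respiratory events, hypotension, nausea and vomiting it includes "constipation, drowsiness, confusion, delirium or other mental status changes, myoclonus, headache, urinary retention". Outcomes are documented at the end of the stay. No interval, checklist, definition or assessor is given for the symptom items.

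**Dosing before oral transition.** In PDA, IV doses are as-needed orders, at 4-hour intervals for pain 4-6 and, for severe pain, "IV hydromorphone 0.6 mg Q2H PRN for pain 7-10". In PCA the base order is "IV Hydromorphone 0.1 mg Q10 minutes", with as-needed rescue at 2-hour intervals for breakthrough pain. After transition both arms have the same oral regimen. Both arms also have "PO Acetaminophen 1000 mg Q8H scheduled".

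**Analysis (B3.B, Data Analysis).** Categorical variables are compared by Pearson's chi-square at 0.05.

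**The concern.** Oximetry and vital signs can detect respiratory decompensation and hypotension. They do not detect nausea, headache, myoclonus, constipation or urinary retention, and they detect drowsiness or confusion only indirectly. Whether such a symptom is charted depends on whether the patient volunteers it or a member of staff notices or asks.

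The randomised factor is the mode of opioid delivery, and that mode can change how often staff are at the bedside during the IV phase. Staff also know the assignment: no blinding is described, and the hospitalist is told the arm. The opportunity to record a symptom may therefore differ by arm, and within an arm between the IV and oral phases. The chi-square comparison takes recorded events at face value. A difference could appear where none exists, or a true one could be hidden. Uneven capture cannot be repaired after discharge.

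**Working it through.** The plan gives no adverse event rate or detection probability, so there is no figure of its own to reproduce on this point. The only design figure used is 87 per arm, which was derived for length of stay. The normal formula gives 2 × (1.96 + 0.842)² / 0.42² = 89, close to 87; 87 is used below as the plan states it.

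**1. Possible nurse contacts per day in the IV phase, from the orders in B3.A**

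- Common to both arms: 24/4 = 6 rounds for vital signs and pain score, plus up to 24/8 = 3 for acetaminophen if given separately, so 6 to 9.
- PDA as-needed doses: 0 up to 24/4 = 6 (pain 4-6) or 24/2 = 12 (pain 7-10), before any rescue. A 4-hourly dose may coincide with the round and add nothing.
- PCA: none for base doses; rescue 0 up to 24/2 = 12.

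The gap thus ranges from none to substantial. Doses and frequencies are stated to be recommendations only.

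**2. What unequal contact could do (all detection inputs assumed)**

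True incidence is set equal in both arms. Recorded rate = true incidence × detection probability. The results are exact rejection probabilities of the uncorrected chi-square test, two-sided 0.05, 87 per arm. PDA is given more contact here only for illustration; exchanging the arms gives the same probabilities.

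*Model A: one episode, noticed only if a nurse is present.* Detection = min(1, symptom hours / hours between contacts). Contacts every 2 h in PDA and 4 h in PCA, true incidence 40%:

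| Symptom duration | Recorded PDA v PCA | Significant |
|---|---|---|
| 1 h | 20% v 10% | 45% |
| 2 h | 40% v 20% | 83% |
| 3 h | 40% v 30% | 28% |
| 4 h or more | 40% v 40% | 5% |

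At 20% true incidence, the 1-hour case gives 10% v 5% and 23%. With contacts every 3 h v 4 h at 40% incidence, durations of 1, 2 and 3 h give 10%, 18% and 28%.

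*Model A with repeat episodes.* With k independent 1-hour episodes, detection = 1 − (1 − 0.50)^k v 1 − (1 − 0.25)^k. For k = 2, 5, 8 and 10 the results are 50%, 21%, 8% and 6%.

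*Model B: each contact has a fixed chance q of recording an existing symptom.* Detection = 1 − (1 − q)^contacts, with 12 contacts v 6:

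- q = 0.10: detection 0.72 v 0.47, recorded ratio 1.53, significant 34%.
- q = 0.30: detection 0.99 v 0.88, recorded ratio 1.12, significant 8.9%.

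**3. Equal detection.** Detection of 0.80 in both arms gives 5.0% at 40% true incidence. A common schedule restores the nominal level to the extent that it equalises detection.

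**The case against.** The case on the other side is substantial.

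- The plan does name these symptoms for monitoring in both arms, and the components it lists need not be exhaustive. This stands: the gap is that method and interval are unspecified, not that monitoring is absent.
- Both arms share the 4-hourly vital-sign and pain-score rounds and the 8-hourly acetaminophen. All PDA doses are as needed, those for pain 4-6 fall at the same interval as the round, and PCA has its own 2-hourly rescue. The documents do not say who gives each dose or whether symptoms are asked about then. This stands and limits the possible gap.
- Symptoms that persist or recur over a stay are likely to be caught eventually; the 4-hour and repeat-episode rows above bear this out.
- The issue touches part of one of twelve secondary outcomes. Length of stay, naloxone use, ICU transfer and mortality do not depend on symptom questioning.

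A reader might go further and infer that PCA patients have almost no nurse contact, so that PCA will look safer than it is. The documents do not support this. Rescue doses and shared rounds provide contact in PCA. B5 singles out the pump for intoxication risk, and in an unblinded trial that may draw closer attention to PCA patients and raise detection there. Nor should any single figure, such as the 45% in the 1-hour row, be taken as an estimate.

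What survives is that the plan has no common procedure that would make the recorded rates comparable, whichever way any imbalance runs.

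**Conclusion.** The point holds in limited form. The plan compares symptom events between arms without a common schedule for ascertaining them, in a trial with no described blinding and a randomised factor that can alter bedside contact. Recorded rates may differ without a true difference.

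Direction and size cannot be determined from the documents. The illustrations at 40% true incidence span about 5% to 83% for a spurious significant result, entirely on assumed detection inputs. The effect is largest for brief, isolated symptoms and largely disappears for those lasting 4 hours or more or recurring often. The primary outcome is not affected. This should be changed because the remedy is cheap and the loss cannot be recovered later, but it does not threaten the trial's main comparison.

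**What to change.** In B3.A, under the recommendations for all patients:

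1. Add a short, fixed yes/no check of the symptom items of outcome (e) to the existing 4-hourly pain-score and vital-sign round. Word each item to cover the period since the last round, so that brief events between rounds are not lost. Use the same form in both arms and in both the IV and oral phases.
2. State in secondary outcome (e) and in Data Analysis that the main between-arm comparison of symptom events rests on this check.
3. Report events noted at other times by arm as well, alongside the main comparison.

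The cost is a small amount of extra charting at a round that already takes place. The check equalises the opportunity to record a symptom. It does not remove judgement by staff who know the assignment, and a brief sign that neither patient nor nurse noticed can still be missed.

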#### **B3. DESCRIPTION OF RESEARCH PROTOCOL**

A. Study Design – Overview, Methods, Procedures

- We will identify patients with AP based on the 2012 revised Atlanta criteria for diagnosis,
   i.e., AP is diagnosed if 2 out of the following 3 criteria are met:
- Acute onset of persistent, severe, epigastric pain often radiating to the back,
- Elevation in serum lipase or amylase to three times or greater than the upper limit of normal,
- Characteristic findings of acute pancreatitis on imaging (contrast-enhanced computed tomography [CT], magnetic resonance imaging [MRI], or transabdominal ultrasonography).
- Patients will be recruited for participation in this study while they are hospitalized with AP at Beth Israel Deaconess Medical Center. Once the patient has been transferred from the ED to the hospital floor, we will identify and recruit them for participation in our study.
- After obtaining informed consent from the patient, the patient will be enrolled by simple randomization to either the PCA or the PDA arm of the study. The research staff will assign patients to either the PCA arm or the PDA arm based on a standard randomization. Once, a patient has consented, the research staff will assign them to the next sequential study ID and corresponding study arm and let the attending hospitalist know of the result. The patient will then be enrolled in their assigned arm.
- The initial protocol for analgesic administration in each arm is as follows:

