#### B. Statistical Considerations

# a. Sample Size Justification:

- Data from a retrospective study of acute pancreatitis patients receiving either patient-controlled analgesia (PCA, n=116) or conventional IV push (IVP, n=647) showed that mean length of stay was higher in the PCA group (9.9 ± 7.14 days) compared to the IVP group (6.4 ± 9.86 days). The effect size calculated using this data yielded a Cohen's d=0.42. Therefore, assuming a 5% error probability for two groups, the estimated sample size to achieve 80% statistical power was determined to be 87 patients per group. At the midpoint of the study when half of target sample size is reached, preliminary post-hoc analysis will be performed to determine effect size and statistical power.

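### Patients who cannot tolerate their assigned analgesia mode and switch are dropped from the analysis, so length of stay is not compared as randomised and their events are missing from the results

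*Combined protocol and SAP*

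**What the plan says.** The rule is in B3.A, under Recommended for all patients. It applies to a patient who is "unable to tolerate either the PDA or the PCA arm for any reason and requires switching over to the other arm" as part of clinical care. Of such patients the plan says "they will be withdrawn from the study and their data will be excluded while analyzing the results".

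Other text that bears on the point:

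- **Open label.** Assignment follows consent and simple randomisation, and research staff then "let the attending hospitalist know of the result" (B3.A, Overview). This is unavoidable when the two arms are different delivery modes.
- **Limits on switching.** The same section says "the mode of IV opioid administration (PDA vs PCA) should remain as assigned until transition to PO opioid", while doses may vary within the mode. Both arms have rescue and step-up orders.
- **Monitoring.** "Each patient will be closely monitored for adverse events related to opioid" administration, so bedside surveillance covers everyone.
- **Outcomes.** The primary outcome is length of stay in days. Secondary outcomes include opioid-related adverse events (e), naloxone and antiemetic use (f), ICU transfer (h), "30-day readmission rates" (i) and mortality (j, k).
- **Analysis.** B3.B.b names the t-test, the Mann-Whitney test and the chi-square test. It does not name an analysis population.

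**The concern.** This is an exclusion made after randomisation, on a criterion that depends on how the patient responded to the assigned treatment. Patients with pain that is hard to control, or with troublesome side effects, could plausibly have a different length of stay from the rest. If they leave one arm more often than the other, or if a different kind of patient leaves each arm, the groups that remain are no longer exchangeable. A difference in length of stay could then reflect who was removed. B4 only hypothesises better pain control with PCA, so unequal switching is possible but not documented.

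The second problem is safety, and it does not depend on any bias in length of stay. The exclusion covers all of a switcher's data without exception. A patient taken off PCA because of respiratory decompensation would not appear in the adverse-event results, although B5 itself names acute opioid intoxication as a risk of the pump. The gap is in the reported results, not at the bedside.

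B2 says that no prospective trial of this comparison exists. The randomised comparison is the trial's main contribution, and this rule weakens it.

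**Working it through.** **1. The plan's own figure.** From B3.B.a: d = 0.42, 5% error, 80% power, 87 per group. The plan does not state sidedness; two-sided is assumed.

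n per group = 2(1.960 + 0.842)² / 0.42² = 15.70 / 0.1764 ≈ 89.

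This is close to the stated 87. By the noncentral t, 87 per group gives 78.7% power. The sample size makes no allowance for excluded patients.

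**2. Shift in length of stay.** Let q be the proportion of an arm that switches and k the mean stay of switchers minus that of non-switchers. The full arm mean is the non-switcher mean plus q × k, so dropping switchers lowers the arm mean by q × k:

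- 10% × 3.5 days = 0.35 day
- 20% × 5 days = 1.00 day

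The design difference is 9.9 − 6.4 = 3.5 days, so these shifts are 10% and 29% of it.

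**3. Type I error.** The documents give no q or k, so every scenario is an assumption. The simulation has no true effect, 87 per arm, log-normal stay with mean 6.4 and SD 9.86 (the IV-push figures in B3.B.a) and 20,000 trials per scenario (Monte Carlo standard error about 0.15 to 0.25 points). Switching is linked to stay through a correlated normal score set to give the stated k. Only switchers who stay longer were modelled.

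| Scenario | t-test | Mann-Whitney |
|---|---|---|
| No exclusion | 4.4% | 5.0% |
| 5% in one arm, 2 to 5 days longer | 4.5–4.7% | 5.3–5.4% |
| 20% in each arm, similar patients (5 days longer) | 4.4% | 4.7% |
| 10% in one arm, 3.5 days longer | 5.0% | 5.7% |
| 10% in each arm, 3.5 days longer in one and 0 in the other | 5.2% | 5.9% |
| 20% in one arm, 5 days longer | 9.8% | 11.6% |
| As above, with the PCA figures (9.9, SD 7.14) | 14.7% | 13.7% |

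The fifth row shows that equal switch rates do not by themselves remove the problem: what matters is whether similar patients leave each arm.

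**4. Safety reporting.** With assumed counts, 8 patients with an event among 87 is 9.2%. If 2 of the 8 switch and are dropped, the report shows 6 of 85, or 7.1%.

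**5. Power under each approach.** d = 0.42, two-sided 0.05, switching in one arm only. Exclusion leaves 87 against 83, 78 or 70 patients with d unchanged. Assigned-arm analysis keeps 87 per arm with d × [1 − q(1 − s)], where s is the share of the effect that switchers keep.

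| Switching | Exclusion | Assigned arm, s = 0.5 | Assigned arm, s = 0 | Break-even s |
|---|---|---|---|---|
| 5% | 77.7% | 76.6% | 74.4% | 0.76 |
| 10% | 76.4% | 74.4% | 69.8% | 0.72 |
| 20% | 73.9% | 69.8% | 59.6% | 0.72 |

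Assigned-arm analysis has the higher power only when s exceeds the break-even value. Power is therefore not an argument for the change.

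**The case against.** The strongest case on the other side is about size. Switching may be rare: the mode is meant to stay as assigned, doses can be adjusted within it, rescue and step-up orders exist in both arms, and patients whose encephalopathy or psychiatric illness would prevent PCA use are not eligible. If IV opioids are needed again after oral transition, the assigned mode is resumed. With 5% switching, or with similar patients leaving both arms, the error rate barely moves. Rates of about 9 to 15% need extreme inputs that no section supports. The simulations also consider only longer-staying switchers, although the direction is unknown. All of this stands, and it limits what can be said about magnitude. It does not offset the rule, and the provision on resuming the assigned mode does not concern switchers.

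B1 speaks of patients receiving each mode, which fits a per-protocol question. That supports having such an analysis, but not having it as the only one.

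The rule governs the analysis and does not forbid a descriptive listing of switchers' events. That is true, but no section provides for one, and as written the outcome results omit them.

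Finally, an assigned-arm analysis cannot include a length of stay that is never observed because the patient withdrew consent to data collection before discharge. That point is fair, and the amendment should deal with it.

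**Conclusion.** The concern holds, and the rule must be changed before any analysis, including the planned midpoint look. Confidence is high that the exclusion is wrong as written: it undoes the randomised comparison of the primary outcome on a treatment-related trigger, and it removes switchers' events from the safety results. Confidence about the size is low. The documents give no switch rate, no reasons and no switcher outcomes, so the bias may be negligible and its direction is unknown. Under the assumptions shown, the middle cases are small (type I error about 5 to 6%), and material inflation needs heavy, lopsided switching by patients with much longer stays. The case rests on principle and on complete safety reporting, not on a demonstrated distortion.

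**What to change.** Replace the exclusion sentence in B3.A with text to this effect:

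*Patients who switch mode remain in the study. Outcomes continue to be collected to discharge and day 30 unless the patient withdraws consent to further data collection, in which case data up to withdrawal are used. All randomised patients are analysed in their assigned arm (intention-to-treat).*

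Then:

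- State the same population in B3.B.b, Data Analysis.
- Report safety for all randomised patients, switchers included. A further summary by mode in use is optional.
- Report by arm the number of switches with reasons, and the number of patients whose length of stay is unobserved after consent withdrawal. State in advance how those missing values are handled.
- Keep the analysis without switchers as a supportive per-protocol analysis only.

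The clinical freedom to switch is unchanged.

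The cost is a one-paragraph amendment plus some continued collection. The plan says "At the end of their hospital stay, we will document the following outcomes", and switchers' inpatient outcomes should be recoverable from the hospital record. The satisfaction score and the 30-day outcomes need active follow-up, and the consent text should be checked to see that it allows this. The real downside is power: with 10% switching in one arm, 74.4% or 69.8% (switchers keeping half or none of the effect) against 76.4% under exclusion. That is an acceptable price for a comparison that randomisation protects.

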# b. Data Analysis:

- Primary and secondary outcomes of interest will be studied as outlined above. Data will be presented as mean ± standard deviation, median [interquartile range; range], and count (percentage), as appropriate. Data will be graphed, QQ plots performed and Shapiro-Wilk test utilized to assess for normality. Statistical tests for primary and secondary outcome will be compared using independent samples t-test and Mann-Whitney U test, as appropriate. Categorical variables were investigated using Pearson's Chi-Square. Statistical significance will be assigned at 0.05. All data will be analyzed using the R statistical software.

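### Patients who switch between PCA and PDA are excluded from analysis with no exception for safety, so the by-arm safety comparison covers only those who stayed on their assigned route

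*Combined protocol and SAP*

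**What the plan says.** The rule is in section B3.A of the combined protocol and SAP, under Recommended for all patients. It applies to a patient who is "unable to tolerate either the PDA or the PCA arm for any reason and requires switching over to the other arm" as part of clinical care. For such patients, "they will be withdrawn from the study and their data will be excluded while analyzing the results". The rule covers both directions of switching and all of the patient's data.

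The outcome list that follows in B3.A includes several safety outcomes: opioid-related adverse events (item e, from respiratory decompensation to confusion, delirium, drowsiness and hypotension), "Use of naloxone and antiemetics" (item f), ICU transfer (item h), "All-cause inpatient mortality and opioid-related inpatient mortality" (item j) and 30-day mortality (item k).

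Section B3.B.b says only that "Primary and secondary outcomes of interest will be studied as outlined above". It defines no intention-to-treat, as-treated or safety population.

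The rule reaches only patients who change route. On dosing, B3.A says "The recommended doses are not required for maintenance in the study", so a changed dose or frequency keeps the patient in. So do naloxone within the assigned arm and the move to oral opioids.

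**The concern.** Intolerance of the assigned route can include opioid toxicity, so whether a patient is analysed can depend on the events being compared. Section B5 acknowledges a risk particular to the PCA pump: a large dose in a short time, with possible acute intoxication. If a patient with such an event is then taken off the pump and given physician-directed doses, the event leaves the comparison.

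The resulting table would describe patients who tolerated their route, while appearing to describe everyone randomised. If switching is related to events and differs between arms, a true difference can look smaller or larger than it is, or a difference can appear where there is none. Because the rule withdraws the patient from the study, later events, including 30-day mortality, may not be collected either.

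**Working it through.** **Inputs from the documents.** There are 87 patients per arm (B3.C). The plan's 87 comes from d = 0.42, 80% power and 5% error (B3.B.a). The two-sided normal formula gives n = 2 × (1.960 + 0.842)² / 0.42² = 89 per group, and power at 87 is 79%, so the stated figure is reproduced to within 2 patients. It concerns length of stay and does not decide this point. It is used here only as the denominator.

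**Inputs assumed.** The documents give no event or switching rates. For illustration, the true proportion of patients with a safety event is taken as 10% on PCA and 5% on PDA.

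**Formulae.** In one arm of n patients, let p be the true event proportion, s the share of patients with an event who switch, and u the share of patients without an event who switch.

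- Expected patients with events left in the analysis: n × p × (1 − s)
- Event rate among those retained: p(1 − s) / [p(1 − s) + (1 − p)(1 − u)]

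**Everyone counted.** PCA 87 × 0.10 = 8.7 patients with events; PDA 87 × 0.05 = 4.35. The difference is 5.0 points.

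**Switching on PCA only.** PDA stays at 4.35 patients and 5.0%.

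| s | u | PCA patients with events left | PCA rate among retained | Difference from PDA (points) |
|---|---|---|---|---|
| 10% | 0 | 8.7 × 0.90 = 7.8 | 0.090 / 0.990 = 9.1% | 4.1 |
| 25% | 0 | 8.7 × 0.75 = 6.5 | 0.075 / 0.975 = 7.7% | 2.7 |
| 10% | 10% | 7.8 | 0.090 / 0.900 = 10.0% | 5.0 |
| 25% | 10% | 6.5 | 0.075 / 0.885 = 8.5% | 3.5 |
| 10% | 20% | 7.8 | 0.090 / 0.810 = 11.1% | 6.1 |

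**Reading the table.** Events are lost from the count whenever s is above zero. The rate within an arm is understated when s exceeds u, unbiased when they are equal and overstated when s is below u. Switching because of toxicity raises s. Switching because of uncontrolled pain can raise u. The direction therefore depends on why patients switch, in each arm, and the documents do not say. If no patient with an event switches, the event counts are unaffected.

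**The case against.** The strongest objection is that toxicity need not lead to a switch. Both arms use hydromorphone with the same ceiling of 1 mg per hour and 3 mg per 4 hours. B3.A provides responses within the arm (naloxone and free adjustment of dose and frequency) and says that the mode should stay as assigned until oral transition. Moving from PCA to PDA means larger single doses of the same drug, 0.4 to 0.6 mg against 0.1 mg, which is not an obvious answer to overdose. Toxicity leading from PDA to PCA is harder still to justify. This stands as a limit on size: large switching shares among affected patients have no support in the documents. It does not remove the rule, which is written for any cause.

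It can also be said that the effect is small beside the trial's imprecision. At 10% switching, 0.9 of 8.7 expected patients is lost, and 87 per arm gives only about 24% power for 10% against 5% even with everyone counted (normal approximation, two-sided 0.05). That is fair, but low precision is no reason to accept an avoidable selection as well.

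Three stronger readings are tempting, and the documents do not support them.

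- A reader might infer that the rule will hide harm from PCA. The direction is unknown: switching for pain can offset or reverse the shift, as the table shows.
- A reader might infer that switchers' events go unwatched. B3.A requires bedside monitoring of each patient, and the exclusion concerns analysis of results. Event reporting may also be described elsewhere, since this file is labelled Part B of a study description. Neither puts a switcher's event back into the by-arm comparison.
- A reader might infer that a midpoint safety review is compromised or needs to be added. B3.B.a places a look "At the midpoint of the study when half of target sample size is reached" and gives its purpose as estimating effect size and power. No midpoint safety comparison is described, and whether to have one is a separate question.

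**Conclusion.** The concern holds as a matter of text. An explicit rule removes all data from anyone who switches, no section exempts safety outcomes, and the by-arm safety comparison is therefore conditional on staying on the assigned route.

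The size and direction of any bias cannot be derived. Under the assumed 10% and 5% event rates, with 10% to 25% of affected PCA patients switching, the PCA rate among retained patients lies between 7.7% and 9.1% if nobody else switches. It lies between 8.5% and 10.0% if 10% of unaffected PCA patients switch too. The first pair understates the true 10%; the second pair runs from a modest understatement to no bias.

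The point is worth an amendment because the correction is cheap and leaves fewer assumptions behind the safety table, not because harm is known to be concealed. The same sentence also removes switchers from length of stay and every other outcome; that is outside this point.

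**What to change.** Amend the switching rule in B3.A so that a patient who changes route stays in the study for safety. Count every safety outcome on the B3.A list for all randomised patients by assigned arm, where consent allows: all of item e, naloxone use, ICU transfer, and inpatient and 30-day mortality. Naming only the gravest events would leave out confusion, delirium, drowsiness and hypotension, which are plausible reasons for stopping PCA. State the same population in B3.B.b.

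In the safety table, give the reason for each switch (toxicity, uncontrolled pain, other) and whether each event came before or after it. If a safety comparison is made at the midpoint, use the same population there; no new midpoint table or review is asked for.

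The cost is a short amendment and one extra table, built from outcomes already listed. The main drawback is that events after a switch are attributed to the arm originally assigned; the before/after column lets the reader see how many these are. If the exclusion was meant only for efficacy, one clarifying sentence to that effect would begin the same amendment.
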